**Background:**

Embryonic aneuploidy is the underlying etiology for the majority of failed implantation and miscarriage. Preimplantation genetic screening (PGS) with transfer of a euploid embryo has been advocated as a strategy for increasing live birth rates with a single embryo transfer. Culturing embryos to the blastocyst stage for trophectoderm biopsy is a requirement for PGS. Several commercially-available single-step embryonic culture media with varying composition have been established for use in the IVF laboratory. Early reports have suggested differences in clinical outcomes, such as aneuploidy and miscarriage rates, with distinct culture media currently in standard use. However, there have been no clinical trials demonstrating the superiority of any one commercially-available culture media formulation. As a result, clinics use media with varying composition based upon familiarity and cost.

**Specific Aims:**

1. To determine if aneuploidy rates differ between sibling embryos cultured in distinct media.
2. To determine if embryo quality differs between sibling embryos cultured in distinct media.
3. To determine if morphokinetic parameters, as assessed by time lapse imaging, differ between sibling embryos cultured in distinct media.
4. To determine if and how morphokinetic parameters and aneuploidy rates differ between embryos with zona breach performed on day three of embryo development versus at the blastocyst stage.
5. To assess the accuracy of non-invasive genetic testing of embryos from spent culture media.

**Design:**

Prospective sibling embryo study in an academic IVF laboratory comparing clinical parameters for embryos cultured in two different single-step culture media with time lapse imaging.

**Study Population:**

Couples planning in vitro fertilization (IVF) with intent for blastocyst culture for preimplantation genetic screening (PGS) will be offered enrollment prior to initiation of their treatment cycle. Intend to enroll 124 subjects (see sample size calculation below).

**Inclusion Criteria:**

All subjects planning blastocyst culture for preimplantation genetic screening (PGS) will be offered enrollment.

AFC  $\geq$ 8

Male and female partner  $\geq$  18 years of age

**Exclusion Criteria:**

Female partner age  $>$ 42 years of age

Cleavage stage biopsy

**Outcome Measures:**

Aneuploidy rate for embryos cultured in one of two distinct media from the same patient (Primary outcome)

Embryo quality at cleavage and blastocyst stages

Morphokinetic parameters from time lapse imaging

**Study Implementation:**

Couples planning in vitro fertilization (IVF) with intent for blastocyst culture for preimplantation genetic screening (PGS) will be offered enrollment prior to initiation of their treatment cycle. Ovarian stimulation will be performed with standard treatment chosen by the couple's primary physician. The day of ovulation trigger will be determined by the primary physician. Oocyte retrieval will be performed according to clinic standard 36 hours following ovulation trigger. All oocytes aspirated from the left ovary will be allocated to Global Media while all oocytes from the right ovary will be allocated to SAGE media (see supplement with media systems). Follicular fluid will be collected from a large and a medium-sized follicle from each ovary in order to perform a direct correlation of follicular size to oocyte recovery, maturation, and embryo development. The collected follicular fluid will also be assayed for estradiol, follicle stimulating hormone, leutinizing hormone, and progesterone.

On the day of oocyte retrieval, the male partner will produce a semen sample per usual clinic protocol. Following 2-3 hours of incubation, hyaluronidase will be used to denude cumulus cells surrounding oocytes per usual clinic protocol. Fertilization will be performed by intracytoplasmic sperm injection (ICSI) of all mature oocytes by a trained embryologist. After 16-18 hours, fertilization will be evaluated by the existence of two pro-nuclei. Fertilized embryos from each patient's cohort will remain split for culturing in SAGE or Global media systems as previously designated. All embryos will be cultured in the EmbryoScope+ time lapse incubator. Once placed in the EmbryoScope, embryos will be cultured at 37 degrees C with 6% CO2 and 5.5% O2 or up to 6 days without media exchange.

The EmbryoScope+ incubation chamber contains a built-in microscope and camera allowing for continuous monitoring of embryonic development. Image acquisition software will be used to obtain high-contrast images every 10 minutes from several focal planes to create time-lapse videos. Conventional embryonic assessment will be made by observations at pre-specified time points. Cleavage-stage embryos will be assessed for cell number, symmetry, percentage fragmentation, evidence of multinucleation, and progression of compaction. Blastocysts will be evaluated to assess for blastocele volume and expansion, inner cell mass development, and trophectoderm organization. Additional morphokinetic parameters will be assessed with time lapse videos including time to pronuclear fading or syngamy (tPNf), time to 2-8 cells, time to morula, start of blastulation, blastocyst, and expanded blastocyst. Cleavage anomalies will be recorded. Zona breach will be performed with the use of a laser per usual clinical protocol on day 3 of embryo development or at the blastocyst stage. All spent media will be collected and sent for quantification of embryonic DNA content.

Embryonic biopsy for preimplantation genetic screening will be performed at blastocyst stage. As per usual clinical protocol, on the day of biopsy, 5-10 trophectoderm cells will be gently aspirated. All embryos making it to the blastocyst stage will be eligible for biopsy, including low quality blastocysts. Arrested embryos may be biopsied to determine a cause for arrest.

Preimplantation genetic screening will be performed per usual clinical protocol by PacGenomics. All embryos will be vitrified following biopsy according to standard clinic protocol awaiting PGS results. Embryos subsequently determined to be euploid will be transferred as a controlled or natural cycle frozen embryo transfer according to standard clinical protocols. Number of embryos to be transferred will be determined by the patient's primary physician.

Additional data will be collected on clinical pregnancy rate (ultrasound demonstrating gestational sac with yolk sac per transfer) and live birth rate. These data are routinely collected and reported to the Society for Assisted Reproductive Technology Clinical Outcomes Reporting System (SART CORS) according to the Fertility Clinic Success Rate and Certification Act of 1992.

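### The primary aneuploid fraction is in practice a fraction among embryos that reach blastocyst, and no blastocyst or euploid-blastocyst yield per oocyte or embryo is planned to read it against

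*Combined protocol and SAP*

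**What the plan says.** Aim 1 is worded "To determine if aneuploidy rates differ between sibling embryos cultured in distinct media". Outcome Measures names "Aneuploidy rate for embryos cultured in one of two distinct media from the same patient (Primary outcome" without a denominator. The other two entries are "Embryo quality at cleavage and blastocyst stages" and time-lapse morphokinetics. Blastocyst formation is not listed.

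Study Implementation assigns the medium by ovary at retrieval. All mature oocytes are injected, two pronuclei are checked at 16-18 hours, and "Fertilized embryos from each patient's cohort will remain split for culturing in SAGE or Global media systems as previously designated". On biopsy it says "Embryonic biopsy for preimplantation genetic screening will be performed at blastocyst stage" and "All embryos making it to the blastocyst stage will be eligible for biopsy, including low quality blastocysts". The next sentence adds "Arrested embryos may be biopsied to determine a cause for arrest". The recorded timings include "time to morula, start of blastulation, blastocyst, and expanded blastocyst".

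Statistical Analysis calls the primary outcome a rate, but the test it specifies is a paired t-test on how many euploid blastocysts each medium produced. Sample Size Calculation calls the outcome a fraction and sizes it in blastocysts: 176 per arm for 29% versus 16% euploid.

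**The concern.** Ploidy for the primary comparison is observed among embryos that survived several days in the medium under test. The medium can shift the ploidy mix of the biopsied embryos in two ways: by changing ploidy, or by changing which embryos reach biopsy. The fraction alone cannot separate them.

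The two explanations lead to different advice for a clinic choosing a medium, which is how Background frames the question. A medium that produces more aneuploid embryos at the expense of euploid ones costs the patient transferable embryos. A medium that only carries additional aneuploid embryos to blastocyst costs none, yet its aneuploid fraction looks worse. The same mechanism could also mask a real difference.

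The planned count of euploid blastocysts is not a sufficient substitute. Without a denominator it reflects how many oocytes each ovary supplied and how well embryos of any ploidy developed. Because the left ovary always goes to one medium and the right to the other, any systematic side difference in oocyte number would appear as a difference between media.

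**Working it through.** **The plan's own figure.** Inputs from Sample Size Calculation are 29% and 16%. Alpha and power are not stated; I assume two-sided 0.05 and 80%.
- Uncorrected n = [1.96·√(2·0.225·0.775) + 0.842·√(0.29·0.71 + 0.16·0.84)]² / 0.13² = 161.
- With the continuity correction, n = 176, which matches. It is a two-proportion calculation on blastocysts, so the fraction is sized conditional on reaching blastocyst.

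**Model for selection.** Let e be the euploid share at fertilisation, and sE and sA the chances that a euploid or aneuploid embryo reaches blastocyst.
- Blastocysts per fertilised embryo = e·sE + (1−e)·sA
- Euploid blastocysts per fertilised embryo = e·sE
- Euploid fraction among blastocysts = e·sE / [e·sE + (1−e)·sA]

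The documents give none of e, sE or sA. Every value below is an assumption, with e the same in both media so that neither medium affects ploidy. The plan's 29% is a fraction in a calculation sized in blastocysts; I borrow it for e only as a convenient number.

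| Assumed case | Formation | Euploid among blastocysts | Euploid yield |
|---|---|---|---|
| e 0.29, sE 0.60, sA 0.40 vs 0.60 | 45.8% vs 60.0% | 38.0% vs 29.0% | 17.4% vs 17.4% |
| e 0.30, sE 0.60, sA 0.45 vs 0.55 | 49.5% vs 56.5% | 36.4% vs 31.9% | 18.0% vs 18.0% |
| e 0.29, sE 0.60 and sA 0.40 vs both multiplied by 1.2 | 45.8% vs 55.0% | 38.0% vs 38.0% | 17.4% vs 20.9% |
| e 0.29, sE 0.60 and sA 0.40 vs sE 0.50 and sA 0.441 | 45.8% vs 45.8% | 38.0% vs 31.7% | 17.4% vs 14.5% |

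First row in full: 0.29 × 0.60 = 0.174. Then 0.174/(0.174 + 0.71 × 0.40) = 0.174/0.458 = 0.380, and 0.174/(0.174 + 0.71 × 0.60) = 0.174/0.600 = 0.290.

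- Rows 1 and 2: the fraction differs by 9.0 and 4.5 points with no effect on ploidy and no loss of euploid embryos.
- Row 3: proportional survival leaves the fraction unchanged but raises the euploid count.
- Row 4: formation is equal, yet the fraction differs by 6.3 points through selection alone. The euploid yield shows a difference that formation does not.

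**Wider range.** With 50-70% aneuploid at fertilisation, sE = 0.60 in both media, and sA of 0.30 vs 0.40, 0.30 vs 0.50 or 0.40 vs 0.60, the spurious gap runs from about 7 to 13 points.

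**What would imitate the whole planning effect.** With equal euploid survival, turning 29% into 16% needs aneuploid embryos to reach blastocyst (0.84/0.16)/(0.71/0.29) = 5.25/2.448 = 2.14 times as often in one medium.

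**Chance of significance, for scale only.** At 176 per arm, an unpaired comparison that ignores clustering gives, for row 1, SE = √[(0.380·0.620 + 0.290·0.710)/176] = 0.0501, z = 0.0899/0.0501 = 1.79, power about 43%. For row 2, SE = 0.0505, z = 0.045/0.0505 = 0.89, power about 14%. The plan specifies no such test, and equal arms are a simplification.

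**The count test in row 1.** With equal embryo numbers, say 10 fertilised per medium, expected euploid blastocysts are 10 × 0.174 = 1.74 in each, so the paired t-test has nothing to detect. With 8 against 6 fertilised embryos (assumed), they are 8 × 0.174 = 1.39 and 6 × 0.174 = 1.04, a gap of 0.35 that comes only from supply.

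**The case against.** The strongest reply is that the written analysis does not make the error. The only primary test specified counts euploid blastocysts, and with equal embryo numbers per medium that count does not move when a medium merely carries more aneuploid embryos forward. This is correct. A reader might infer that following the plan to the letter would lead it to blame such a medium; the documents do not support that. The problem attaches to the rate or fraction, which Outcome Measures, Statistical Analysis and Sample Size Calculation all name as primary. The count has the separate weakness of lacking a denominator.

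Other objections:
- A reader might infer that ploidy is known for blastocysts and nothing else. Arrested embryos may also be biopsied. That is optional, serves another purpose and has no stated role in the primary analysis, so it does not remove the selection.
- A reader might infer that formation goes unmeasured. Injection, the two-pronuclei check and time to blastocyst are all recorded, so it is unplanned rather than unavailable. The planned count of high quality blastocysts does not replace it: it leaves out the low quality blastocysts that are eligible for biopsy and has no denominator.
- Aim 1 asks whether rates differ, and no section says a medium causes aneuploidy. That conclusion is a risk of interpretation.
- Testing ploidy at blastocyst is inherent to this setting. True, and the remedy is to report what the fraction is conditional on, not to change the biopsy.
- The illustration needs aneuploid survival to change while euploid survival stays fixed. This stands as a limit on any claim about size.

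**Conclusion.** The point holds as a gap in outcomes and interpretation. The primary fraction is conditional on an event after allocation that the medium can affect, and neither the bare fraction nor the undenominated count answers Aim 1 alone.

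The size of the bias cannot be computed from the documents. On assumed survival rates the spurious difference runs from zero (proportional survival) through about 4.5 points to 9 points, and up to about 13 in the wider range, against a planning difference of 13 points.

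A reader might also infer that a difference in fraction can be credited to ploidy whenever blastocyst formation is similar in the two media. The fourth row of the table shows that it cannot: equal formation does not exclude selection. The added yields put the fraction in context and show whether euploid embryos are lost; they do not by themselves identify an effect on ploidy.

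**What to change.** In Outcome Measures and Statistical Analysis, add two supporting outcomes by medium:

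1. Blastocysts per injected mature oocyte and per 2PN embryo.
2. Euploid blastocysts per injected mature oocyte and per 2PN embryo.

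Analyse both within patient using those denominators, for example with a binomial model that has a medium effect and accounts for patient. Of the two denominators, the injected oocyte is closer to allocation, since fertilisation also follows it.

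State that biopsies of arrested embryos stay out of the primary rate or are reported separately. State also that a difference in aneuploid fraction will be described as a difference among biopsied blastocysts and read alongside the two yields, not reported as an effect of the medium on ploidy. Do not add a rule that attributes the difference to ploidy when formation does not differ.

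The cost is a few lines of analysis text and two extra tables. The data are already recorded, and no procedure changes.

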#### **Statistical Analysis:**

The primary outcome is rate of aneuploidy for embryos cultured in one of two distinct media from the same patient. We will perform a paired t-test to compare number of euploid blastocysts in embryos split for culture in two different media from the same patient. Our secondary outcome is embryo quality for split embryos. Embryo quality will be graded at the cleavage and blastocyst stages. High quality cleavage embryos will have at least 6 blastomeres or greater and scores of "1" or "2" for symmetry and fragmentation. Expanded blastocysts will be considered high quality where inner cell mass and trophectoderm score are "A" or "B." We will perform paired t-tests to compare number of high quality cleavage and blastocyst stage embryos from the cohort of sibling embryos cultured in different media.

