#### **Sample Size Calculation:**

The primary outcome is aneuploid fraction for embryos cultured in two distinct media from the same patient. To detect same difference in euploid fraction as Hickman et al (29% vs 16%) we would need 176 blastocysts per arm. This calculation does not account for clustering of embryos from the same patient; however, we will obtain a substantially higher number of blastocysts per arm as we are planning to power for our secondary outcome (see below).

Our secondary outcome relates to differences in embryo quality among split embryos cultured in distinct media. Previous review of internal data demonstrates that interventions targeting couples with a history of poor embryo quality have been able to demonstrate a four-fold increase in high quality day 3 fraction. We need 62 subjects (31/arm) to detect four-fold increase in high quality day 3 fraction within this population with history of poor embryo quality (< 40% good quality cleavage stage fraction). We estimate that 25% of clinic patients have poor quality cleavage stage fraction. Therefore, we would need  $4 \times 62 = 248$  patients. However, since we are splitting embryos from the same patient, each cohort of embryos serves as its own control. Therefore, we need to enroll **124 patients** to power for our secondary outcome of clinically meaningful differences in embryo quality.

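### The primary outcome is an aneuploidy rate, but the primary test compares numbers of euploid blastocysts, so a difference in blastocyst yield can pass for, or hide, a difference in aneuploidy

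*Combined protocol and SAP*

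**What the plan says.** Every description of the primary outcome is a rate or fraction:

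- Outcome Measures: "Aneuploidy rate for embryos cultured in one of two distinct media from the same patient (Primary outcome".
- Statistical Analysis: "The primary outcome is rate of aneuploidy for embryos cultured in one of two distinct media from the same patient".
- Sample Size Calculation: "The primary outcome is aneuploid fraction for embryos cultured in two distinct media from the same patient", followed by a requirement of 176 blastocysts per arm to detect a euploid fraction of 29% vs 16%.
- Specific Aims, Aim 1: "To determine if aneuploidy rates differ between sibling embryos cultured in distinct media". The aims are not ranked, but this is the one that the primary outcome serves.

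The test comes in the sentence directly after the Statistical Analysis definition: "We will perform a paired t-test to compare number of euploid blastocysts in embryos split for culture in two different media". No denominator, offset, weighting or fraction-based analysis is given anywhere.

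On allocation, Study Implementation says: "All oocytes aspirated from the left ovary will be allocated to Global Media while all oocytes from the right ovary" go to SAGE. The split is kept after fertilisation, and every embryo that reaches blastocyst is eligible for biopsy.

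The secondary outcome shows a similar, milder mismatch. The test is on counts ("We will perform paired t-tests to compare number of high quality cleavage and blastocyst stage embryos"), while the sizing is on a fraction ("We need 62 subjects (31/arm) to detect four-fold increase in high quality day 3 fraction").

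**The concern.** The number of euploid blastocysts in an arm is the number of blastocysts times the fraction that are euploid. A test on that number never uses the aneuploid blastocysts, so it cannot tell a better fraction from a larger yield.

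Pairing removes differences between patients. It does not remove an average difference between arms. Because the left ovary always goes to Global and the right to SAGE, and numbers are not rebalanced at the two-pronuclei stage, any mean difference in yield by side or by medium enters the primary test. The protocol itself treats an effect of medium on development as open: Aims 2 and 3 ask whether embryo quality and morphokinetics differ. The primary test should not depend on those answers being null.

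Two errors are possible. The test may reject when aneuploidy rates are identical, or miss the planned difference when the better medium gives fewer blastocysts. In either case the result could not be attributed to ploidy.

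**Working it through.** **1. The plan's own figure.** Inputs from Sample Size Calculation: p1 = 0.29, p2 = 0.16, difference d = 0.13, mean 0.225. Two-sided 5% and 80% power are assumed, since the plan states neither.

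- Without continuity correction: n = [1.960 × √(2 × 0.225 × 0.775) + 0.842 × √(0.29 × 0.71 + 0.16 × 0.84)]² / 0.13² = 160.8, so 161.
- With continuity correction: (n/4) × [1 + √(1 + 4/(n × d))]² = (160.8/4) × [1 + √(1 + 4/20.9)]² = 175.8, so **176**.

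The plan's 176 is therefore reproduced as a comparison of two proportions. The figure is not at fault. It shows that the outcome was sized as a fraction and is tested as a count.

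**2. What the count test compares.** Expected difference per patient = yield₁ × p₁ − yield₂ × p₂. Illustrative yields:

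- Same fraction, different yield: 3 × 0.50 − 2.4 × 0.50 = 0.30 euploid blastocysts per patient, with no difference in aneuploidy.
- Different fraction, offsetting yield: 5.44 × 0.16 − 3 × 0.29 = 0.87 − 0.87 = 0, although the full planned difference is present.

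**3. Error rates by simulation.** From the plan: 124 patients; fractions 29%, 16% and their mean 22.5%. Assumed: 2, 3 or 4 blastocysts per ovary on average; Poisson counts with a shared gamma patient effect (CV 0.5); a shared patient effect on the logit of euploidy (SD 0.7); two-sided 5%; a 50% euploid fraction as a second setting. There were 20,000 trials per setting. The comparator is a patient-stratified Mantel-Haenszel test, which is the score test of conditional logistic regression.

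Count test, rejection with *identical* euploid fractions (%, at 2 / 3 / 4 per ovary):

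| One arm yields more by | fraction 22.5% | fraction 50% |
|---|---|---|
| 0% | 5.0 / 5.0 / 4.9 | 5.0 / 4.6 / 4.9 |
| 5% | 6.0 / 6.2 / 6.5 | 6.8 / 7.5 / 8.3 |
| 10% | 7.8 / 9.4 / 11.0 | 11.8 / 15.7 / 18.6 |
| 20% | 16.5 / 23.5 / 30.0 | 31.9 / 45.2 / 55.7 |
| 30% | 30.8 / 43.3 / 54.0 | 58.6 / 76.3 / 86.9 |

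The stratified test stays at 4.8-5.3% throughout. If the 20% gap is instead coded as one arm yielding 20% *fewer*, the count test rejects in about 20-64% over both fractions. Random left-right imbalance with equal means (log-SD 0.5 per ovary) leaves the count test at 4.9-5.2%.

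Power for 29% vs 16% (%, at 2 / 3 / 4 per ovary):

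| Yield of the better medium | count test | stratified test |
|---|---|---|
| equal | 86.2 / 96.3 / 98.9 | 88.5 / 98.3 / 99.7 |
| 10% fewer | 68.3 / 85.0 / 93.2 | 86.4 / 97.5 / 99.7 |
| 20% fewer | 43.1 / 59.7 / 72.1 | 83.5 / 96.3 / 99.5 |
| 20% more | 98.6 / 99.9 / 100.0 | 91.3 / 98.9 / 99.9 |
| equal means, random imbalance | 79.9 / 90.5 / 95.4 | 84.7 / 96.9 / 99.5 |

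In the row with 20% more, the count test's extra power comes from yield, not ploidy.

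**4. A different model.** With log-normal patient yields (log-SD 0.5), logit SD 0.5 and 4,000 trials, identical fractions and yields of 3 vs 2.4 give rejection in 34% (fraction 29%) to 51% (fraction 50%). Fraction-based tests stay near 5%. With 16% vs 29% and yields of 5.4 vs 3, the count test rejects in about 5%, and fraction-based tests in 97% or more.

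**The case against.** The mismatch in wording is not in dispute. The case on the other side concerns its consequence and the remedy.

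- *No yield gap is shown.* Nothing in the documents states or implies a mean difference by side or medium, and with equal means the count test holds 5% and loses little power. This stands, and it makes every error rate above conditional. But the design does not ensure equal yield, and the test would not reveal a gap.
- *The high figures rest on a 50% euploid fraction.* This also stands: the only fractions in the documents are 29% and 16%. At 22.5%, the range for a 20% gap is 17-30%, which is still three to six times the nominal level.
- *A fraction is not immune either.* The stratified test's 5% holds because the simulation makes yield independent of ploidy. If a medium changes which embryos reach blastocyst, the fraction among biopsied blastocysts shifts too. That is a limit on interpretation. It is not a reason to test the count.
- *A count difference caused by the medium is a real and useful effect.* True, but it is not an effect on the aneuploidy rate, and it suits a supporting analysis.
- *A paired t-test on per-patient fractions would be enough.* It does cure the inconsistency and holds 5%. It has less power: 79.4 / 93.5 / 97.9% at equal yield, against 88.5 / 98.3 / 99.7%.
- *The secondary mismatch is weaker.* Agreed. Aim 2 and Outcome Measures say only embryo quality, and no calculation was made for it.

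**Conclusion.** The concern holds. The sole primary test is on a different quantity from the stated primary outcome, and this must be corrected before the data are analysed. That conclusion rests on the text alone and is firm.

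The size of the harm is conditional on a systematic yield difference that the documents neither give nor rule out. Under the assumed model it is negligible at equal mean yield and small at a 5% gap (6-8% false rejection). It is material at 20%: 17-30% false rejection at the plan's mean fraction, and power for the planned difference down to 43-72% when the better medium yields 20% fewer. Random imbalance that averages zero does not inflate type I error, and costs the count test 4 to 6 points of power relative to the stratified test.

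**What to change.** In Statistical Analysis, replace the primary test with a within-patient comparison of aneuploid vs euploid among biopsied blastocysts that have a PGS result. One suitable choice is logistic regression conditional on patient with medium as the effect, reporting the odds ratio and a Mantel-Haenszel rate difference stratified by patient, each with a 95% confidence interval. A mixed or GEE logistic model with patient as the cluster is an acceptable alternative. A paired t-test on per-patient fractions is the minimum. Fix one method before results are seen.

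Also:

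- State that biopsied arrested embryos are tabulated separately.
- Keep euploid blastocysts per injected mature oocyte as a supporting analysis. It would reveal, but not remove, selection to blastocyst that depends on medium.
- As a minor point, analyse high quality embryos as a fraction, to match the sizing.

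The cost is a wording change and a standard model on data already collected. In a conditional analysis, patients with blastocysts in only one medium add nothing (about 27%, 16% and 10% at 2, 3 and 4 per ovary under the assumed model). Counting also patients with no blastocysts and those whose blastocysts are all euploid or all aneuploid, about 58%, 43% and 33% add nothing at a 22.5% fraction. The power figures above already include this loss. A mixed or GEE model would keep the patients with blastocysts in one medium only.

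None of this separates medium from ovary side, which remain fully confounded by the allocation.

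### The primary outcome is an aneuploidy fraction, but the planned test compares a count of euploid blastocysts, which is not its complement and can differ between media when aneuploidy does not

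*Combined protocol and SAP*

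**What the plan says.** The Outcome Measures section lists the aneuploidy rate by medium as primary. The Statistical Analysis section agrees: "The primary outcome is rate of aneuploidy for embryos cultured in one of two distinct media from the same patient". The sentence after it gives the test, a "paired t-test to compare number of euploid blastocysts" from the split cohort. The Sample Size Calculation section calls the outcome a fraction, "The primary outcome is aneuploid fraction for embryos cultured in two distinct media from the same patient", and then sizes on the opposite call: "To detect same difference in euploid fraction as" a cited sibling study, 29% versus 16%, for which "we would need 176 blastocysts per arm".

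Three quantities therefore stand for one outcome: an aneuploid fraction, a euploid fraction and a euploid count.

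On what is biopsied, the Study Implementation section says: "All embryos making it to the blastocyst stage will be eligible for biopsy, including low quality blastocysts". Genetic testing follows the usual clinical protocol. The documents do not list the result categories, define the denominator of the rate, or say how a biopsy without a result is handled. Mosaic results are not mentioned. Oocytes from the left ovary go to one medium and those from the right ovary to the other, so the number of embryos per medium is not equalised within a patient.

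**The concern.** A euploid count mirrors an aneuploid fraction only if both media yield the same number of blastocysts and every blastocyst is called either euploid or aneuploid. The plan secures neither.

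- **Denominator.** A medium, or an ovary, that yields more blastocysts will show more euploid ones at the same aneuploid fraction.
- **Third category.** A no-result biopsy is neither euploid nor aneuploid. In a euploid count it scores zero, as an aneuploid embryo does. The same is true of a mosaic result if the laboratory reports mosaic as a separate class.

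Changing the count to euploid blastocysts over all blastocysts would cure the first problem and leave the second.

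At stake is the meaning of the primary result. A significant test could be read as a difference in aneuploidy when it reflects yield or biopsy failure. Because low-quality blastocysts are biopsied and embryo quality is itself an outcome compared between media, a no-result share that differs by medium is possible. The documents do not show that it occurs.

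**Working it through.** **1. The plan's own figure.** Alpha and power are not stated. Assume two-sided 5%, 80% power and a continuity correction, with p1 = 0.29, p2 = 0.16 and mean 0.225:

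n = [1.960·√(2·0.225·0.775) + 0.842·√(0.29·0.71 + 0.16·0.84)]² / 0.13² = 160.8, or 161.

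With the correction, n' = (160.8/4)·[1 + √(1 + 4/(160.8·0.13))]² = 175.8, or 176. This matches. One-sided 5% with 90% power and no correction gives 175, so the inputs are inferred. Using the complements (71% versus 84%) gives the same answer: on a two-call scale, swapping euploid for aneuploid does not alter the sample size.

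**2. Effect of the missing denominator.** From the documents: "Intend to enroll 124 subjects". Assumed: Poisson blastocyst numbers with means 3.0 and 2.5 per medium, 40% aneuploid in both, no failed results.

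- Mean euploid counts: 3.0 × 0.60 = 1.80 and 2.5 × 0.60 = 1.50, a difference of 0.30.
- Standard error: √(1.80 + 1.50)/√124 = 1.817/11.14 = 0.163.
- Ratio: 0.30/0.163 = 1.84, which implies roughly 45% rejection at two-sided 5%.

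Simulation (4000 trials) gave 44%, and 41% with 10% failed results in both media. Counting aneuploid blastocysts instead does not help (34% and 30%). A paired test on the aneuploid fraction gave 5% in both settings.

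**3. Effect of no-result biopsies.** Assumed: 124 patients, Poisson mean 2.5 blastocysts in each medium, patient-level aneuploid probability Beta with mean 0.45 and a+b = 5, the same in both media. One medium has a 5% no-result share and the other varies. There are two bounding cases: (I) failure is independent of ploidy; (N) every such result comes from a non-aneuploid embryo.

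Expected gap in the euploid share at 5% versus 15%:

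- Case I: 0.55 × (0.95 − 0.85) = 5.5 points.
- Case N: (0.55 − 0.05) − (0.55 − 0.15) = 10 points.

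Approximate rejection of a paired t-test at two-sided 5%, with no true difference in aneuploidy:

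| No-result share | I: euploid count | I: aneuploid count | I: aneuploid / conclusive | N: euploid count | N: aneuploid / conclusive |
|---|---|---|---|---|---|
| 5% v 5% | 5% | 5% | 5% | 5% | 5% |
| 5% v 10% | 8% | 8% | 5% | 15% | 8% |
| 5% v 15% | 15% | 14% | 5% | 45% | 17% |
| 5% v 20% | 31% | 26% | 5% | 80% | 33% |

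The fraction of conclusive results holds its level when failure does not depend on ploidy. In case N it is still disturbed, though less than the count. If the case N results are mosaics that stay in the denominator as not aneuploid, the aneuploid fraction is equal in both media by construction and the disturbance disappears. No-result and mosaic therefore need separate rules.

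**4. Patients lost to a paired ratio.** With mean 2.5 and a 5% no-result share, the chance that a medium has no conclusive result is e^(−2.375) = 0.093. At 5% in both media, 1 − 0.907² = 18% of patients lack a ratio in one medium or the other. At 5% versus 20% it is 1 − 0.907 × (1 − e^(−2.0)) = 1 − 0.907 × 0.865 = 22%.

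**The case against.** The strongest reply is that harm requires yield or no-result shares that differ by medium, and the documents give no rates and no evidence of a gap. Biopsy of low-quality blastocysts applies to both media. That stands: at equal yield and equal shares the planned test keeps its 5%.

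A reader might also infer that any failed or mosaic result is scored as aneuploid and so creates a false difference. The documents do not support that. They do not show the laboratory's categories. It may return only two calls, class some mosaics as euploid, or re-biopsy failures. The mosaic part is conditional. The no-result part is firmer, because a blastocyst without a euploid call cannot enter a count of euploid blastocysts.

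Nor should 45% and 80% be read as the expected size. They need every failed result to spare aneuploid embryos, which nothing in the documents suggests; with independent failure the figures are 15% and 31%. It is equally tempting to say that testing aneuploid calls would hold 5%. For counts that is true only in the same extreme case.

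Finally, the no-result issue can be called a detail beside the missing denominator. On the assumed figures the denominator is the larger part, but one definition settles both.

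**Conclusion.** The mismatch is in the text: the outcome is an aneuploidy fraction, the test is on a euploid count, and no rule covers results that are neither call. The count can differ between media when aneuploidy is equal, through yield (about 40% rejection at an assumed 3.0 versus 2.5 blastocysts) or through unequal no-result shares (about 8% to 31% for 5% versus 10% to 20% under independent failure, and up to about 15% to 80% in the extreme case). All these rest on assumed rates, so they show what could happen, not what will. The figure of 176 blastocysts per arm is unaffected by this point. The plan's separate admission, "This calculation does not account for clustering of embryos from the same patient", is not resolved by it either. The definition is worth settling before results are seen; the point does not show that the trial will reach a wrong conclusion.

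**What to change.** In the Statistical Analysis section, replace the euploid count with aneuploid calls divided by blastocysts with a conclusive result, per patient and medium. Compare it within patient, by a paired analysis or a binomial model clustered by patient.

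- Leave no-result biopsies out of numerator and denominator, and report their share by medium so that a reader can judge whether failure may depend on medium.
- State the laboratory's result categories. If mosaic is one of them, fix before results are seen whether it counts as aneuploid, and add a sensitivity analysis counting it the other way.
- Use the same definition in the Outcome Measures and Sample Size Calculation sections.

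The cost is protocol wording and, if mosaic is reported, one sensitivity analysis; no new data are needed. No-result blastocysts leave the denominator, and a per-patient paired ratio drops patients with no conclusive result in one medium (about 18% to 22% under the assumptions above). A clustered model keeps them and is preferable for that reason.
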